### Step 2: Develop and refine the Itch CBT protocol.

Qualitative data from Step 1 will be analyzed systematically using a constant comparative approach . Trained coders will independently generate a preliminary list of emergent themes . Next, the coders will meet to discuss initial thoughts, insights, and observations for the development of initial coding categories. Through a systematic analysis process, analysts will continually refine themes by collapsing redundant and removing irrelevant themes and suggested treatments. Once no new categories have emerged, coding dictionaries will be developed for the remaining analysis . We will construct a saturation grid to track themes as they emerge and determine when no new relevant information is obtained. Coded data will be summarized and the most important themes in terms of prevalence and/or impact will be identified. These themes, data representing the themes in the words of patients and families, will form the basis for the Itch CBT intervention.

The study team and key stakeholder (National Eczema Association) will then meet and agree to the best protocol to target and address themes related to itch rumination generated during qualitative interviews. The result of Aim 1 will be a standardized protocol that can be tested in Aim 2.

### **5.3 Aim 2 Study Design**

#### Step 3 Implement CBT Itch compared to usual care in a RCT.

Based upon the interviews conducted in Aim 1, patients with atopic dermatitis reported significant concerns in addition to preoccupation with itch and scratching, specifically regarding social difficulties, anxiety, sleep challenges, and difficulty with concentration. Thus, the treatment was expanded to address these multiple areas of concern. Additionally, parents of patients reported significant concerns about scheduling office appointments because of absences from work and school due to multiple appointments for medical providers. For this reason, it was decided that the primary method of intervention would be provided via telemedicine.

## Brief Cognitive Behavioral Therapy to Treat Itch Rumination “Itch CBT” in Eczema

We plan to recruit 24 patient-parent dyads (48 total participants) stratified by child’s age ( $n = 6$ : 8-12,  $n = 6$ : 12-17 years) to the CBT itch rumination intervention. Usual care will be provided to 12 AD patients, matched on gender and itch severity. Itch severity will be based on the NRS Itch Severity score. Potential participants will be recruited from Lurie Children’s Dermatology and Allergy Departments. If patients have an upcoming clinic (or remote clinic visit) scheduled, they will be contacted prior to their clinic visit by a study coordinator/provider and will be provided with a brief description of the study to determine interest in order to allow patients to schedule sufficient time for study activities following their clinic appointment. If patients do not have an upcoming clinic visit, they will be contacted by phone by a study coordinator/provider and given a brief description of the study. If interested, participants will be screened using the inclusion/exclusion criteria (see Screening Questionnaire). If eligible, patients will be e-consented to the study using REDCap e-consent procedures by a study coordinator. A study coordinator will email a link to the e-consent form to the participant and then thoroughly explain the study, allowing time for participants to ask questions. If participant is still interested, they will be instructed to sign the e-consent form using the link. After participants have been e-consented, they will be randomized to one of the study conditions (usual care vs. CBT). Following e-consent, participants will be emailed a copy of their signed e-consent form. Following their clinic appointment, all participants will complete study questionnaires (see Table of Assessments below).

**Randomization Procedures:** Participants will be randomized to one of two groups: (1) Itch CBT or (2) Usual care. Randomization will occur on a 1:1 ratio and within strata, which are gender (male vs. female) and Itch Numerical Rating Scale (4-6 vs. 7-10). Participants will be randomized to treatment based on a predetermined list within each strata created using the *blockrand* package of R. Randomization will occur by blocks, with varying block sizes, in accord with recommended methods for RCTs. The randomization key will be linked to a unique study ID number, as well as to a treatment condition (Itch CBT vs. Usual Care). Participants will be aware that there are different arms they can be assigned to and will know which randomization group they are assigned.

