### 4.0 Inclusion and Exclusion Criteria

#### 4.1 Inclusion Criteria:

1. Moderate to severe atopic dermatitis [assessed by Patient Oriented Eczema Measure (POEM) score of >-8 OR NRS itch score of >= 4].

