## 5.0 Procedures Involved

### 5.1 Overall Study Design

The overall study design is to develop a brief CBT intervention tailored to itch rumination via qualitative methods, including creating an interview guide with closed- and open-ended questions for stakeholders concerning itch-related distress and rumination. From these interviews, the itch rumination CBT will be created to address common fears and anxiety around itch, ruminative thoughts concerning itch, and other correlates associated with lowered quality of life in AD. This intervention will then be tested in a pilot RCT to compare the brief CBT intervention to usual care. Although therapists will not be blinded to intervention group, the research assistant assessing and analyzing outcomes with patients and their caregiver will be blinded to which intervention they received. Figure 1 summarizes our interventional model of CBT Itch.

Target Population: A convenience sample of children (8-17 years) with moderate-severe AD (and one parent) will be recruited from our group’s multidisciplinary AD clinic.

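### Minor, cheap improvement: nothing requires the baseline CDLQI to be completed before families learn their arm, so the model's premise of no treatment influence at baseline is not secured for that outcome

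*Combined protocol and SAP*

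**What the plan says.** The recruitment text in section 5.3 describes screening, e-consent and then allocation: "After participants have been e-consented, they will be randomized to one of the study conditions (usual care vs. CBT"). The questionnaires come next: "Following their clinic appointment, all participants will complete study questionnaires". The same text also recruits families who have no appointment: "If patients do not have an upcoming clinic visit, they will be contacted by phone by a study coordinator/provider". For them no questionnaire time is given.

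The Randomization Procedures paragraph says that participants "will know which randomization group they are assigned", without saying when they are told. The strata are "gender (male vs. female) and Itch Numerical Rating Scale (4-6 vs. 7-10"), so an itch rating must exist before allocation, at least as a band. Eligibility (section 4.1) rests on a POEM "score of >-8 OR NRS itch score of >= 4". Neither step calls for a CDLQI.

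The children's Table of Assessments schedules the CDLQI at Visit 1, Visit 4 and Follow-Up. Section 5.4 names NRS Itch Severity and the CDLQI as primary outcomes, and its response profile analysis posits no treatment influence before treatment. Section 5.1 states that "the research assistant assessing and analyzing outcomes with patients and their caregiver will be blinded to which intervention they received".

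**The concern.** Randomisation makes the arms' expected baselines equal only for values that knowledge of the arm cannot yet have affected. Children and parents report these outcomes themselves and know their arm, so blinding the research assistant does not protect the answers. If a family learns its arm and then completes the baseline CDLQI, hope or disappointment could move the score. A model that treats the arms as equal at baseline would carry part of that movement into the treatment effect. Section 2.0 plans to attribute differences in change over time to the intervention, so the baseline carries weight.

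The remedy is available only beforehand. Once baseline answers have been collected after disclosure, no analysis of the same data can fully restore the premise.

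**Working it through.** **Order of events.** Set side by side, the texts give:

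- Itch rating: a stratification factor, so at least its band is known before allocation. Section 5.4 does not name this value as the analysis baseline, and the documents do not say whether the raw score is stored.
- CDLQI: first listed at Visit 1. No earlier CDLQI is described. Screening refers to a separate form ("screened using the inclusion/exclusion criteria (see Screening Questionnaire")) that is not among the documents, so its content cannot be checked.
- First therapist contact: section 1.0 counts four sessions, the CBT Arm text places surveys after each therapy session, and the compensation table pays Visit 1 as a therapy visit. Together these can put CBT-arm Visit 1 surveys after a first session. But section 1.0 also describes the first visit as assessing difficulties, and the CBT Arm text describes an assessment followed by three sessions, which allows the other reading.
- Instrument: section 5.4 and the recruitment and randomisation text speak of an itch NRS. Both Tables of Assessments list an Itch Severity VAS and no itch NRS.

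**Sample size used.** Section 5.3, as read here: 6 + 6 = 12 to CBT, plus 12 to usual care = 24 dyads; 24 x 2 = 48 participants, which agrees with the stated total. The documents give no alpha, SD, correlation or effect size.

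**Assumptions.** 12 per arm, unit SD, no true effect, two-sided 5% test, baseline to follow-up correlation rho of 0.3 to 0.7, and a shift b in Visit 1 answers (CBT minus usual care). Neither the size nor the direction of b is known.

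**Formula.** With baseline means treated as equal, the estimate is approximately (follow-up difference) - rho x (baseline difference).

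*Case A: the shift affects Visit 1 only.* Bias = 0 - rho x b = -rho x b. At b = 0.25 this is -0.075, -0.125 and -0.175 SD for rho 0.3, 0.5 and 0.7. Simulation (40,000 runs per setting, ANCOVA with estimated slope) gave:

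| b | Adjusted bias, rho 0.3 / 0.5 / 0.7 | Rejection, rho 0.3 / 0.5 / 0.7 |
|---|---|---|
| 0.10 | -0.03 / -0.05 / -0.07 | 5.1% / 5.0% / 5.5% |
| 0.25 | -0.07 / -0.13 / -0.18 | 5.4% / 6.6% / 8.5% |
| 0.50 | -0.15 / -0.25 / -0.35 | 6.5% / 10.0% / 19.2% |

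The SD of the estimate with no shift is about 0.40, 0.36 and 0.30. If the CBT arm reports the worse baseline, the bias favours CBT; if usual care does, it runs against CBT. With a baseline taken before disclosure, b = 0 at baseline and this bias is 0.

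*Case B: the same shift persists at follow-up.* Under the present order the error is b - rho x b = (1 - rho) x b. With a clean baseline it is b. At b = 0.25 the present order gives 0.175, 0.125 and 0.075 SD; the clean baseline gives 0.25 SD throughout. At b = 0.5, simulated rejection is about 13%, 10% and 7% to 8% under the present order, and about 22% to 36% with a clean baseline.

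**Can the data tell the cases apart later?** Post-only minus adjusted is 0 - (-rho x b) = rho x b in Case A and b - (1 - rho) x b = rho x b in Case B. The difference is the same, so comparing the two analyses cannot show which case holds.

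**The case against.** **The order is partly inferred.** The recruitment text ties randomisation to e-consent and the questionnaires to the clinic appointment; it never ties one to the other. It is not strictly chronological, since the emailing of the signed consent is mentioned after randomisation. Section 5.4 speaks of pre-treatment assessments, not pre-randomisation ones, and a form completed before therapy fits that word. All of this stands. It is why the point is that the premise is not secured. A reader might infer that the baseline CDLQI is contaminated, or that CBT-arm Visit 1 surveys follow a first session. The documents support neither.

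**The effect is small.** At b = 0.1 it is negligible, and at b = 0.25 the bias is at most about 0.6 of the SD of the estimate (0.18 / 0.30). The trial is a pilot. This stands, and sets the grade at minor.

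**The fix can enlarge the error.** Case B shows this, and the arithmetic is right. Participants know their arm at every later visit, so persistence is plausible. It is still no reason to keep the present order, which offsets follow-up bias only by accident, only in part, and only if the shift happens to persist. A clean baseline leaves one limitation that can be stated plainly: unblinded follow-up reporting.

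**The itch baseline has an instrument problem.** This also stands. Locking an NRS helps only if the follow-up instrument is the same.

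**Conclusion.** The point holds as a minor, inexpensive improvement. The documents do not require Visit 1 CDLQI answers before disclosure or before therapist contact, so the premise of the primary model is unsecured for that outcome. For itch the position is better, because a rating must precede allocation, but that value is not named as the baseline and the instrument name differs between sections.

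For a shift confined to Visit 1, the bias is 0.07 to 0.18 SD at b = 0.25 and reaches 0.35 SD, with about 19% rejection, only at b = 0.5 and rho 0.7. These figures rest on assumed b and rho, 12 per arm and a 5% two-sided test. Two further inferences go too far: that such a shift will occur, and that moving the baseline restores the nominal error rate whatever happens later. The second is true only in Case A.

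**What to change.** 1. In the recruitment text of section 5.3, require the CDLQI and the child's itch severity item to be completed and locked in REDCap after e-consent, before allocation is released and before the study therapist's first contact. The remaining Visit 1 forms may follow.
2. Reconcile the itch instrument's name (NRS or VAS) across sections 5.3 and 5.4 and the Tables of Assessments, so that baseline and follow-up use the same instrument. Then name the locked values in section 5.4 as the pre-treatment assessment for both primary outcomes.
3. Reconcile section 1.0, the recruitment and CBT Arm texts in section 5.3, and the compensation table on whether CBT-arm Visit 1 surveys precede the first session. State the questionnaire timing for families with no clinic appointment.
4. Add a sentence that later outcomes remain unblinded self-report, which this change does not cure.

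**Cost.** Protocol wording and one REDCap release rule. Both forms are already due at Visit 1, which carries 12 child and 9 parent instruments; only two need to come first. Allocation and therapist booking come slightly later, although section 1.0 wants the first visit to follow the clinic visit at once, so a therapist slot may have to be held before the arm is known. Consented families who do not complete the two forms are not randomised, which matters with 24 dyads planned.

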## Brief Cognitive Behavioral Therapy to Treat Itch Rumination “Itch CBT” in Eczema

behavioral, and relaxation strategies to combat itch rumination. With expert input from the National Eczema Association and our research team, we have formalized a protocol for Itch CBT. In our second aim, we will pilot the protocol in a brief (4 session) intervention as part of an interdisciplinary AD clinic, comparing Itch CBT to usual care (our standard educational handouts).

Because each group will have similar levels of eczema severity and will be receiving the same level of medical care, we will be able to attribute changes over time between the two groups to this mental health intervention. We predict that patients treated with Itch CBT will show significantly less itch and less severe itch, as well as significantly greater quality of life, at follow-up compared to those receiving standard treatment. Predicted secondary outcomes include decreased rumination on itch, sleep disturbance, depression, and anxiety, as well as improved medication adherence, and social/family functioning. This pilot study will allow us to measure itch rumination, its effects on children with AD, and the efficacy of Itch CBT in itch rumination. With this preliminary data, we can apply for NIH funding to provide more extensive evidence for the efficacy of Itch CBT in treating itch rumination; ideally we hope to develop an Itch CBT protocol that can easily be implemented by trained personnel in the clinic setting or even as an online tool for patients. The National Eczema Association is the perfect partner for our research team to help develop and disseminate this intervention.

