### **For participants randomized to the Usual Care Arm:**

Participants randomized to the Usual Care arm of the study will receive eczema educational materials that are typically provided by their health care provider after a clinic (or telehealth) visit. Examples include an eczema action plan that is created by the provider with the patient and includes daily skincare as well as special skincare instructions for eczema flares, handouts on recommendations for dry skin, etc. Participants in the Usual Care arm will complete the same schedule of study surveys (see Table of Assessments below) as participants randomized to the CBT arm.

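### The Section 5.3 sequence implies, without stating it, that families know their arm before the clinic appointment, and no record of treatment changes is planned to check the equal-care premise

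*Combined protocol and SAP*

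**What the plan says.** All references are to the combined protocol and SAP.

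- **Recruitment, scheduled visit (Section 5.3).** Patients with an upcoming visit are approached in advance: "they will be contacted prior to their clinic visit by a study coordinator/provider". The stated purpose is to gauge interest and "to allow patients to schedule sufficient time for study activities following their clinic appointment".
- **Recruitment, no scheduled visit (Section 5.3).** "If patients do not have an upcoming clinic visit, they will be contacted by phone by a study coordinator/provider". No clinic appointment is defined for this group.
- **Randomisation (Section 5.3).** After screening and e-consent, "After participants have been e-consented, they will be randomized to one of the study conditions (usual care vs. CBT"). Timing relative to the visit is not given.
- **Baseline (Section 5.3).** The next step in the account is "Following their clinic appointment, all participants will complete study questionnaires".
- **Knowledge of arm.** Under Randomization Procedures, participants "will know which randomization group they are assigned". Section 5.1 leaves therapists unblinded and blinds the research assistant who handles outcomes. It does not mention the treating eczema provider.
- **Usual care (Section 5.3).** The materials given after a visit include "an eczema action plan that is created by the provider with the patient".
- **Attribution (Section 2.0).** The two groups are expected to have similar severity and "will be receiving the same level of medical care, we will be able to attribute changes over time between the two groups" to the intervention.
- **Data collected (Section 5.3, assessment tables).** Neither the child nor the parent table has a row for prescriptions, treatment changes or concomitant medication. The nearest item, VAS Dose, is taken at all five time points from child and parent but is not defined.

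**The concern.** Itch severity and CDLQI, the two primary outcomes, can be expected to respond to eczema treatment. If the clinic appointment comes after allocation, any change of treatment made there is a post-randomisation event, decided with a family that knows its arm. A family assigned to usual care might ask for more medical treatment. If the provider knows the arm, a change might be deferred for a child about to start CBT. Either would make medical care differ between arms for reasons linked to allocation.

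Section 2.0 uses equal care as one of two grounds for crediting a difference to CBT. The plan has no procedure to standardise that care and no data item that would show whether it was equal. At the end of the trial the investigators could report a difference between assignments but could not show how much of it reflected different prescribing.

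This is separate from the timing of the baseline questionnaires. Moving those ahead of allocation would still leave the treatment decision after it.

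**Working it through.** **1. Order of events.** Section 5.3 can be set out by recruitment route.

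| Step | Visit scheduled | No visit scheduled |
|---|---|---|
| Contact | before the visit | by phone |
| Screening, e-consent | next in the account | next in the account |
| Randomisation | after e-consent; not tied to the visit | after e-consent |
| Clinic appointment | implied after randomisation | none defined |
| Questionnaires | after the appointment | said to follow an appointment that is not defined |

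For the first route the natural reading is allocation, then appointment, then baseline. Section 1.0 places the first CBT session directly after a telehealth clinic visit. That is easiest to arrange if the arm is already known, but it is compatible with either order.

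**2. What the planned data could show.** VAS Dose appears to be an adherence item. Adherence is not a record of prescribing, and improving it is one aim of the CBT sessions, so it cannot stand in for a check of equal care. The initial therapist assessment asks about adherence, but only in the CBT arm. Section 5.4 names no adjustment or sensitivity analysis for treatment changes.

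**3. Size, as an illustration.** The documents give no rate of treatment change and no effect of one, so both are assumed. Arm size: Section 5.3 gives 24 dyads, 1:1 allocation, 6 + 6 in the CBT arm and 12 in usual care; 6 + 6 + 12 = 24, so 12 per arm.

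If k more children in one arm have a treatment change, each lowering the itch rating by d points, the shift in the arm difference is k × d / 12.

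| | d = 2 | d = 3 | d = 4 |
|---|---|---|---|
| k = 1 | 0.17 | 0.25 | 0.33 |
| k = 2 | 0.33 | 0.50 | 0.67 |
| k = 3 | 0.50 | 0.75 | 1.00 |

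**4. Chance imbalance alone.** Suppose known allocation has no influence and each child has the same probability p of a treatment change. With A and B independent Binomial(12, p), the exact probabilities are:

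| p (assumed) | P(arms differ by 3 or more) | P(arms differ by 4 or more) |
|---|---|---|
| 0.2 | 0.197 | 0.071 |
| 0.3 | 0.263 | 0.116 |
| 0.4 | 0.297 | 0.143 |
| 0.5 | 0.307 | 0.152 |

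An imbalance of 3 children would therefore arise in about 20% to 31% of such trials even without arm-driven behaviour. The planned data would not reveal it.

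**The case against.** The strongest reply is that the order is inferred. No sentence puts randomisation before the visit. The advance contact is described only as gauging interest and reserving time after the appointment, and the activities in that reserved time could include consent and randomisation. Sentence order is weak evidence, since the emailed copy of the consent form is also described after randomisation. This stands: the documents imply the sequence for patients with a scheduled visit but do not state it, and it cannot be read onto patients without one.

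A reader might also infer that providers prescribe knowing the arm. The documents do not support that. A provider may make the first contact, but a coordinator obtains consent, and nothing says the treating provider learns the allocation. Nor is the action plan shown to be written after allocation; it is an example of routine material.

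A reader might further infer that the primary comparison is invalid. It is not. Section 5.4 specifies intention-to-treat, and care that differs after allocation is part of the effect of assignment. Some differences in the use of treatment are intended, because the sessions cover adherence and planning for flares.

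Two further replies have some force. Section 2.0 rests attribution on similar severity as well as on equal care. Treatment information may also sit in documents not available here, such as the screening questionnaire, or in the clinical data that Section 6.0 mentions without describing. Neither supplies a check of equal care in the plan as written.

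Finally, later allocation does not protect treatment decisions at subsequent visits, when families still know their arm. That is correct, and it is why the treatment record is needed as well as the change of timing.

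**Conclusion.** The concern holds in a limited form. For patients with a scheduled visit, the sequence implies allocation, known to the family, before the appointment, so treatment decisions there can follow it. The equal-care premise in Section 2.0 cannot be checked, because no change in prescribed treatment is recorded. The consequence is weaker attribution of a difference to CBT; the comparison of assignments remains valid.

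The 0.17 to 1.0 point range rests wholly on assumed values of k and d and on 12 children per arm. It shows what an unrecorded imbalance could do and is not an estimate of what will happen. The top of the range needs three excess changes in one arm, each worth 4 points. The chance calculation likewise assumes p.

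This is a worthwhile, inexpensive improvement to a pilot whose results are meant to support a funding application. If randomisation in practice already follows the appointment, the timing part is settled by saying so; the missing treatment record remains.

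**What to change.** 1. **Section 5.3, recruitment.** Keep contact, screening and consent before the visit. State that for patients with a scheduled visit the allocation is released from the predetermined list only once the appointment is finished. Changes made at that visit then precede allocation, and any imbalance in them is due to chance.
2. **Patients with no upcoming visit.** State that they are randomised after consent and the baseline questionnaires, and amend the sentence that ties everyone's questionnaires to an appointment.
3. **Assessment tables.** Add one REDCap item to every survey in both arms: change in eczema prescription since the last survey, yes or no, what changed, and the date. At the first survey, word it to cover the index appointment.
4. **Section 5.4 and Section 2.0.** Report the changes by arm, and make the attribution statement conditional on that table. It would also help to state whether the treating provider is told the arm.

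**Cost.** Some protocol wording and one extra survey item. Therapists are assigned slightly later, which may loosen the Section 1.0 plan for the first session to follow directly on the clinic visit. Treatment changes at later visits are recorded but not prevented.
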